#### Insomnia:

The severity of insomnia symptoms is measured using three self-report symptom inventories with each data collection visit (Appendix A). This includes the Insomnia Severity Index (ISI), the Pittsburgh Sleep Quality Index (PSQI), and the Epworth Sleepiness Score (ESS). The ISI is a 7 question measure, with responses from 0-4 for each question, yielding scores ranging from 0-28 (Bastien, Vallieres, & Morin, 2001; C.M. Morin, Belleville, Belanger, & Ivers, 2011; C. M. Morin et al., 2009). The PSQI is a 19 item inventory that assesses sleep quality over a 1-month time interval (Buysse, Reynolds, Monk, Berman, & Kupfer, 1989). Items are weighted on a 0-3 interval scale. A global PSQI score is calculated by totaling the seven component scores, providing an overall score ranging from 0 to 21, where lower scores denote a healthier sleep quality. The ESS measures a person's general level of daytime sleepiness, or their average sleep propensity in daily life. The simple questionnaire is based on retrospective reports

of the likelihood of dozing off or falling asleep in a variety of different situations. Rated on a 4-point scale (0-3), it evaluates their usual chances of dozing off or falling asleep while engaged in eight different activities. The ESS score (the sum of 8 item scores, 0-3) can range from 0 to 24 (Johns, 1991).

### **Behavioral and Psycho-physiological function:**

#### Depression:

The Center for Epidemiologic Studies Depression Scale (CES-D) is a depression scale which will help to assess this co-morbidity. CES-D is a 20-item survey assessing affective depressive symptomatology to screen for risk of depression (Radloff, 1977). Scores range from 0-60, with a score of 16 commonly used as a clinically relevant cut-off (SmarrK.L., 2003).

#### Anxiety:

The Generalized Anxiety Disorder-7 (GAD-7) is a seven item screening tool for anxiety that is widely used in primary care. GAD-7 is a brief, reliable and valid measure of assessing generalized anxiety disorder (Spitzer, Kroenke, Williams, & Lowe, 2006).

#### Stress:

The Perceived Stress Scale (PSS) is a ten-item psychological instrument for measuring the perception of stress. It is a measure of the degree to which situations in one's life are appraised as stressful. Items were designed to tap how unpredictable, uncontrollable, and overloaded respondents find their lives. The scale, with answers rated from 0-4, also includes a number of direct queries about current levels of experienced stress (Cohen, Kamarck, & Mermelstein, 1983).

### **Quality of Life:**

#### Quality of Life:

The Quality of Life Scale (QOLS) is a 16-item scale that was modified from a 15-item scale used in chronic disease patients. Topics include different components of daily life such as relationships, community engagement, personal fulfillment, and recreation. Each item is scaled from 1 to 7 and a sum score is calculated to represent higher levels of satisfaction in life (range is 16-112) (Carol S. Burckhardt & Anderson, 2003; C. S. Burckhardt, Woods, Schultz, & Ziebarth, 1989; Offenbacher, Sauer, Kohls, Waltz, & Schoeps, 2012).

#### Alcohol Intake Screening:

The AUDIT-C is a short, 3-item alcohol screening for hazardous drinkers or active alcohol use disorders. This measure consists of 3 questions to assess an individual's alcohol use. Each question has five possible answers ranging from 0-4 with a total scoring scale of 0-12. A total score of 3 or more in women and a score of four or more in men is suggestive of hazardous drinking or active alcohol use disorders. This form is modified from the longer, 10-item AUDIT instrument (Bradley et al., 2003; Bradley et al., 2007; Bush, Kivlahan, McDonell, Fihn, & Bradley, 1998).

## **Functional Measures:**

### **Reaction Testing:**

Reaction testing will be evaluated by a drop-stick, clinical reaction time apparatus. It is constructed from a meter stick covered in friction tape with gradations. The modified meter stick is fixed to a weighted rubber cylinder. The apparatus is placed between the thumb and index finger of the subject and released at a random time during a countdown. The subject catches the apparatus and the distance fallen (cm) is converted to reaction. Following two practice trials, subjects perform eight trials, and a mean distance value is used for analysis. This is repeated with a second set of 8 trials later during the enrollment visit, and the mean distance value from the second trial will be used as the baseline value. Use of the average distance from the second set of trials will be used as the baseline value so as to avoid the impact of learning effect for this test. This simple clinical measure has been evaluated by Eckner et al, and demonstrated utility in testing comparable to computerized testing methods (Eckner, Kutcher, & Richardson, 2010). Our pilot data demonstrate improved reaction testing associated with use of HIRREM for athletes with persisting post-concussion symptoms (C. H. Tegeler et al., 2016).

### **Grip Strength:**

Grip strength will be evaluated using a hydraulic hand dynamometer (Baseline Hydraulic Hand Dynamometer). The mean value of the greatest force generated during three trials will be used for analysis (Roberts et al., 2011).

### **Statistical Analysis:**

Continuous variables will be summarized with standard descriptive statistics, such as quartiles, means, and standard deviations, while categorical variables will be summarized with percentages and frequencies. LMMs will be employed to contrast longitudinal changes in systolic and diastolic blood pressure between the HCC and NCC groups. Mean contrasts will be used to compare the changes in blood pressure between groups from V1 to V3, our primary test of efficacy. Comparisons of changes in all secondary outcomes will be assessed in a similar fashion. Assumption and computation diagnostics will be assessed for all model fits (Cheng, Edwards, Maldonado-Molina, Komro, & Muller, 2010) and model adjustments and outcome variable transformations will be made as necessary. Data will be analyzed using SAS v9.4 (SAS Institute, Inc., Cary, NC) or the R Statistical Computing Environment.

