Methods: This will be a randomized, single site, pilot clinical trial, enrolling up to 40 women, who have at least 5 hot flashes per day (with at least one being categorized as moderate to severe), and who are not taking medications or supplements for management of hot flashes. Participants will be randomly assigned to receive 8-16 sessions over a maximum of 4 weeks of acoustic stimulation linked to brain activity (HIRREM and continued current care, HCC) or will be assigned to a waitlist group (continued current care, CCC). Both groups will continue their other current care throughout. There will be pre- and post-intervention data collection to include physiological outcomes (BP, HR, and measures of autonomic cardiovascular regulation), as well as daily hot flash diaries, Hot Flash Related Daily Interference Scale (HFRDIS), the Menopause Rating Scale (MRS), symptom inventories for insomnia (Insomnia Severity Index, ISI; Pittsburgh Sleep Quality Index, PSQI; and the Epworth Sleepiness Score, ESS), depression (Center for Epidemiological Studies- Depression Scale, CES-D), anxiety (Generalized Anxiety Disorder-7, GAD-7), stress (Perceived Stress Scale, PSS), and a quality of life measure (Quality of Life Scale, QOLS), as well as drop stick reaction testing, and dynamometry for grip strength. Measures will be collected at an enrollment visit (V1). Both groups will then maintain a hot flash diary for 7-14 days, after which the intervention will begin for the HCC group. Post-intervention data collections will be obtained at 4-6 weeks (V2, primary outcome) and 12-14 weeks (V3) following completion of the intervention. Follow up data collection for the CCC group will occur at 10-12 weeks (V2), and 18-20 weeks (V3) after the V1 visit. Both groups will maintain a hot flash diary for 1-2 weeks prior to the V2 and V3 visits. The primary outcome will be differential change in hot flash frequency and severity from

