V1 to V2 between HCC and CCC, based on data from the hot flash daily diary. Following V3, those in the CCC group will be offered the opportunity to cross over to receive a course of HCC within 3 months, and will continue to be followed for data collections at 4-6 weeks (V4), and 12-14 weeks (V5) after completing their crossover HIRREM sessions. Additional mean contrasts will be constructed to evaluate the consistency of any benefit of HIRREM through subsequent visits beyond V3. Comparisons of changes in all secondary outcomes will be assessed in a similar fashion.

Importance: This study will explore the use of HIRREM for vasomotor symptoms associated with menopause in a randomized, clinical trial. The study will confirm feasibility using a closed-loop, acoustic stimulation intervention for a randomized clinical trial in this population, and will also provide estimates of effect size, which might justify larger controlled trials. A positive result would suggest that HIRREM might have benefit as a noninvasive, non-drug alternative for management of vasomotor symptoms. This, over and above the potential benefit from participating in a clinical trial, and interacting with the study personnel and the study environment. The study will also help to identify the characteristics of subgroups that might experience differential effects/benefits from HIRREM.

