### Overview:

[figure not shown]
This will be a randomized, single site, pilot clinical trial. Assuming a potential drop-out rate of 20%, up to 48 subjects will be enrolled to achieve a goal of having at least 40 subjects (20 per group) complete the study, per protocol. Patients who have at least 5 hot flashes per day (with at least one being categorized as moderate to severe) will be eligible to participate.

Those who have no other exclusions, are interested to participate, and provide informed consent will be randomly assigned to receive 8-16 sessions of in-office acoustic stimulation linked to brainwave activity (HCC), over a maximum of 4 weeks, while continuing their other current clinical care, or to continue their current clinical care alone (CCC). There will be pre- and post-intervention data collection to include a daily hot flash diary (to be completed for 7-14 days by both groups) and many secondary outcome measures including completion of the MRS, HFRDIS, measures of autonomic cardiovascular regulation (continuous recording of BP and HR for calculation of measure of HRV and BRS), behavioral symptom outcomes (ISI, PSQI, ESS, CES-D, GAD-7, PSS), quality of life measure (QOLS), and function performance measures (drop stick reaction testing, and grip strength). All measures will be collected at an enrollment visit (V1). Both groups will then maintain a hot flash diary for 7-14 days, after which the intervention will begin for the HCC group. Post-intervention data collections will include an intermediate post-intervention visit (V2, primary outcome, 4-6 weeks after intervention completion for HCC, and 10-12 weeks after V1 for CCC), and a final follow up visit (V3, 12-14 weeks following completion of the intervention for HCC, and 18-20 weeks after V1 for CCC). Both groups will maintain a hot flash diary for 1-2 weeks prior to the V2 and V3 visits. The primary outcome will be reduction in frequency and severity of hot flashes score from V1 to V2. Following V3, those in the CCC group will be offered the opportunity to receive a course of HCC within 3 months (will have another brainwave assessment 0-14 days before beginning sessions), and will continue to be followed for data collections at 4-6 weeks (V4), and 12-14 weeks (V5) after completing their HIRREM sessions.

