#### Number of Subjects:

As a pilot study, in a new cohort of participants, using a wait-list control, we are not able to calculate an accurate sample size. In order to evaluate feasibility and effect size, and allowing for up to 20% drop outs, we will arbitrarily enroll up to 48 subjects to achieve a goal of having 40 subjects complete the study per protocol (estimated 20 per group).

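### Efficacy is worded as a difference in change from V1 with no stated use of the baseline value, which can cost precision at about 20 women per arm

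*Combined protocol and SAP*

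**What the plan says.** The Abstract (Methods) makes hot flash frequency and severity the primary outcome, with this contrast: "V1 to V2 between HCC and CCC, based on data from the hot flash daily diary". The Overview agrees: "The primary outcome will be reduction in frequency and severity of hot flashes score from V1 to V2".

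The Statistical Analysis section names one type of model: "LMMs will be employed to contrast longitudinal changes in systolic and diastolic blood pressure between the HCC and NCC groups". It then says: "Mean contrasts will be used to compare the changes in blood pressure between groups from V1 to V3, our primary test of efficacy". For the rest: "Comparisons of changes in all secondary outcomes will be assessed in a similar fashion". Hot flashes, the diary and V2 do not appear in that section.

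No section names a baseline covariate or says whether the arms share a V1 mean. The only opening comes after the sentence on diagnostics: "model adjustments and outcome variable transformations will be made as necessary".

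The Number of Subjects section aims for 40 completers, about 20 per group, from up to 48 enrolled, and calls this number arbitrary. According to Participants/Subjects, Enrollment Visit and Menopause-related symptoms, women are randomized and told their arm at V1, and keep the baseline diary for the 7-14 days after it.

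**The concern.** Every efficacy comparison is worded as a between-group difference in change from V1. The natural way to program this is an LMM with group, visit and group-by-visit, and a contrast of the V1-to-later change between arms. With complete data that contrast is the difference in mean change scores. It fixes the slope of the follow-up value on the baseline value at 1. If the true slope is lower, subtracting the whole baseline adds noise that a fitted slope would remove.

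The trial is small, and the effect-size estimate is one of its two stated products, with feasibility (Abstract, Importance; Number of Subjects). A wider interval than necessary weakens that estimate, although the baseline data needed to narrow it are already collected.

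This is separate from the larger conflict in the same section, where the outcome (blood pressure), the visit (V3) and the arm label (NCC) disagree with the declared primary outcome. Correcting those three words would still leave the handling of baseline open.

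**Working it through.** **The plan's own figure.** 40 × 1.20 = 48 reproduces the planned enrolment. Dividing by the retained fraction gives 40/0.80 = 50, and 48 × 0.80 = 38.4 completers, about 19 per arm. The target of 40 has no power calculation behind it. I use the plan's n = 20 per arm.

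**Inputs not in the documents.** The correlation ρ between V1 and V2 values and the SDs are not given; the pilot data report only medians, ranges and p values. I assume a range for ρ and, at first, one common SD σ at both visits.

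**Formulas.**
- Difference in change: variance = 2(1−ρ) × 2σ²/n.
- Baseline-adjusted difference: variance = (1−ρ²) × 2σ²/n, multiplied by 1 + 1/(2n−4) = 1 + 1/36 = 1.028 for chance baseline imbalance in a small sample.
- Ratio, adjusted to change: (1+ρ)/2 × 1.028.

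**Results at 20 per arm, in units of σ.** The detectable difference assumes 80% power and two-sided 5%.

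| ρ | SE, change | SE, adjusted | Variance ratio | Detectable, change | Detectable, adjusted |
|---|---|---|---|---|---|
| 0.3 | 0.374 | 0.306 | 0.67 | 1.08 | 0.88 |
| 0.5 | 0.316 | 0.278 | 0.77 | 0.91 | 0.80 |
| 0.7 | 0.245 | 0.229 | 0.87 | 0.70 | 0.66 |
| 0.9 | 0.141 | 0.140 | 0.98 | 0.41 | 0.40 |

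Simulation of 20,000 trials for each ρ gave variance ratios of 0.66, 0.77, 0.87 and 0.98. At ρ = 0.5, 20 adjusted women per arm are worth about 20/0.771 = 26 analysed by change. For an assumed effect of 0.8 SD, power at ρ = 0.5 is 69% by change and 80% adjusted. With 19 per arm the factor is 1 + 1/34 = 1.029, and the ratio at ρ = 0.5 stays at 0.77.

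**Does naming an LMM settle it?** No. With two visits, complete data, ρ = 0.5 and n = 20, generalized least squares with separate V1 means by arm gives variance 0.100σ², the change-score value. With a common V1 mean it gives 0.075σ², the large-sample adjusted value.

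**Unequal SDs.** Let k be the V2 SD divided by the V1 SD. In units of the V1 variance times 2/n, change has 1 + k² − 2ρk and adjusted has k²(1−ρ²). The difference is (1−ρk)², which is never negative, so in large samples adjustment never loses.
- ρ = 0.7, k = 1.3: 0.87 against 0.862, ratio 0.99. With the factor 1.028 it is about 1.02, so there is no gain at 20 per arm.
- ρ = 0.7, k = 0.8: 0.52 against 0.326, ratio 0.63, or 0.65 with the factor.

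**Chance imbalance.** The SD of the baseline difference between arms is √(2/20) = 0.316σ, so P(difference above 0.5σ in either direction) = 0.114. At ρ = 0.5 such an imbalance moves the change-score estimate by (1−0.5) × 0.5 = 0.25σ. This is not a second cost: with equal SDs the extra variance of the change score is exactly (1−ρ)² × 2σ²/n, the variance of this shift.

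**The case against.** The strongest objection is that the plan does not commit to the less precise analysis. A reader might infer that the V1-to-V2 hot flash effect will be tested as an unadjusted difference in change. The documents do not support that: the Statistical Analysis section has no hot flash model, its stated contrast is for blood pressure from V1 to V3, an LMM can be built either way, and model adjustments are left open. Moreover, a change outcome is compatible with adjustment, because adjusting the change for baseline gives the same treatment estimate as adjusting the V2 value. All of this stands. What remains is that the wording points to a change contrast, and that an adjustment chosen after diagnostics is not a pre-specified one.

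A second tempting inference is that entry on a high count forces the baseline slope below 1. The entry count is a self-report at screening, and the baseline diary is a later measurement. Regression due to selection would fall largely between those two, so this argument cannot fix the slope.

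Third, the size of the gain rests on an undocumented correlation. Means over 7-14 diary days could correlate highly, and at 0.9 the saving is about 2%. A larger V2 SD can remove it. This stands, and it is why only a range can be given. It would also be wrong to call the change score biased, since under randomization it is not.

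Finally, the proposed covariate is recorded after women know their arm. That is a real weakness, but it can affect the change score, the adjusted estimate and the common-V1-mean model alike, so it is no reason to leave baseline out of the model.

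**Conclusion.** The point holds as a gap in specification with a better method available. How baseline enters the V1-to-V2 hot flash comparison is not stated, and the usual reading of the wording is a change-score contrast. At about 20 per arm and with equal SDs, adjustment lowers the variance by about 33%, 23%, 13% and 2% at correlations of 0.3, 0.5, 0.7 and 0.9. These correlations are assumptions, as are the equal SDs, complete data, and the 80% power and two-sided 5% level behind the detectable differences. With a high correlation or a clearly larger V2 SD the gain is near zero, and at 20 per arm it could be a loss of about 2% (k = 1.3, ρ = 0.7). The change is worth making because it costs little and the section has to be rewritten anyway. It ranks below the conflict over the primary outcome and visit.

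**What to change.** When the Statistical Analysis section is reconciled with the declared primary outcome, state the hot flash model in full:

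- Outcomes: V2 and V3 values, for frequency and for severity.
- Terms: group, visit, group-by-visit, baseline value and baseline-by-visit. An LMM that includes V1 as an outcome with a common V1 mean in both arms is an acceptable alternative.
- Baseline: the mean per day from the baseline diary.
- Primary estimate: the adjusted HCC minus CCC difference at V2, with its 95% CI.
- Secondary outcomes: the same form, with each measure's own V1 value.

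The cost is a few lines of text and two added terms, baseline and baseline-by-visit. No new data are needed.

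The section should also acknowledge as a limitation that the baseline diary is kept after women learn their arm, so that this knowledge may shift reporting and affect any of these analyses. Moving the notification would be a separate change to trial conduct and is not part of this fix.

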### Hypothesis:

The addition of acoustic stimulation linked to brain activity (HIRREM plus continued current care, HCC) will be associated with greater reduction in the frequency and severity of hot flashes experienced than that seen with continued current clinical care alone (CCC), among patients with perimenopausal and postmenopausal vasomotor symptoms.

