#### Number of HCC Sessions and Length of Study:

All baseline measures, along with a brainwave assessment, will be obtained during an enrollment visit (V1). The intervention will commence 7-14 days later. Participants will receive 8 to 16 in-office intervention sessions over a maximum of 4 weeks. HCC sessions will be about 1.5-2 hours in length. All will receive a total of 6 sessions during the first three days of the intervention period. Following the initial 6 sessions, some sessions may be arranged as singles (one per day), if needed due to schedule issues. Participants will be encouraged to complete the remainder of the intervention sessions within two-three weeks, with a maximum of four weeks to complete the sessions. If done as two sessions per half day, subject involvement will thus require 4-8 half days during the intervention period.

At the primary post-intervention data collection visit, all measures will be repeated. This visit will occur at 4-6 weeks after completion of the intervention for the HCC group, and 10-12 weeks after V1 for the CCC group. A final data collection visit (V3) will occur 12-14 weeks after completion of the intervention for the HCC group, and 18-20 weeks after V1 for the CCC group, with repeat of the outcome measures, but no brainwave assessment. At V3, official study involvement is complete for those in the HCC group, while those randomized to the CCC group will be offered an opportunity to be scheduled to receive a

course of HCC within 3 months. Participants who cross over will have a brainwave assessment 0-14 days before starting sessions. Those who opt to do so will receive a course of in-office acoustic stimulation linked to brainwaves, as described for the HCC group, and will continue to be followed for data collections at 4-6 weeks (V4), and 12-14 weeks (V5), as done during the initial intervention period, after completing their HCC sessions.

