#### Post-Intervention Data Collection Visits:

For participants in the HCC group, participants will return for a post-intervention data collection visit (V2, primary outcome) between 4-6 weeks after completion of the intervention. This will occur at 10-12 weeks after V1 for those in the CCC group. All measures will be repeated, including a brainwave assessment. This visit will require about 120 minutes.

Between 12-14 weeks after completion of the intervention, participants in the HCC group will return for a final data collection visit (V3). The V3 visit will be between 18-20 weeks after V1 for those in the CCC group. All measures other than the brainwave assessment will be repeated for a final time. This will complete the official study involvement for participants in the HCC group, while those in the CCC group will be offered an opportunity to be scheduled to receive a course of HCC, and this will be discussed. This visit will take about 45 minutes.

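### The Statistical Analysis section makes blood pressure from V1 to V3 the primary efficacy test, while the protocol declares diary hot flashes from V1 to V2 as primary

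*Combined protocol and SAP*

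**What the plan says.** The Statistical Analysis section is the only part of the document that describes a model. On efficacy it says "LMMs will be employed to contrast longitudinal changes in systolic and diastolic blood pressure between the HCC and NCC groups", and then: "Mean contrasts will be used to compare the changes in blood pressure between groups from V1 to V3, our primary test of efficacy". It adds that changes in all secondary outcomes will be compared similarly.

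Other sections define the primary outcome differently:

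- **Abstract, Methods paragraph:** "The primary outcome will be differential change in hot flash frequency and severity from"; the same sentence then gives the window, the arms and the data source as "V1 to V2 between HCC and CCC, based on data from the hot flash daily diary".
- **Overview:** "The primary outcome will be reduction in frequency and severity of hot flashes score from V1 to V2". The same section lists the continuous blood pressure recording among the secondary measures.
- **Post-Intervention Data Collection Visits**, for the HCC group: "participants will return for a post-intervention data collection visit (V2, primary outcome) between 4-6 weeks after completion of the intervention".
- **Number of HCC Sessions and Length of Study**, on the visit 4-6 weeks after the intervention (10-12 weeks after V1 for CCC): "At the primary post-intervention data collection visit, all measures will be repeated". It calls V3 the final visit.
- **Hypothesis:** HCC will show "greater reduction in the frequency and severity of hot flashes experienced than that seen with continued current clinical care alone (CCC"). The Primary Objective names the same symptoms and comparator. Neither gives a time point.

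**The concern.** The section an analyst will execute names a primary test that does not answer the trial's stated question. Endpoint and visit both conflict with the declared primary outcome, and the comparator carries a label found nowhere else. Because the analysis section extends its method only to secondary outcomes, the declared primary outcome has no primary model, contrast or multiplicity rule there.

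Two things are at stake. If the section is followed, the headline result concerns blood pressure, which no objective names as an endpoint. If it is not followed, the choice between two recorded definitions could be made after the data are seen. That matters more here because participants learn their group at V1 (Enrollment Visit) and the diary is self-reported, so a fixed primary analysis is one of the few safeguards available.

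**Working it through.** **1. The two versions side by side**

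| Element | Statistical Analysis section | Rest of protocol |
|---|---|---|
| Endpoint | Systolic and diastolic blood pressure | Hot flash frequency and severity (Abstract, Hypothesis, Overview; vasomotor symptoms in Primary Objective) |
| Source | Not stated | Daily diary (Abstract) |
| Window | V1 to V3 | V1 to V2 (Abstract, Overview); V2 marked primary (Post-Intervention Data Collection Visits) |
| Comparator | NCC, undefined | CCC |

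The conflict is in current, unredacted text, and no other section resolves it. Blood pressure is a collected measure (Abstract, Overview, Autonomic Cardiovascular Regulation), but the first secondary objective names heart rate, HRV and BRS, not blood pressure.

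**2. Distance between the two visits**

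V2 and V3 timings come from Post-Intervention Data Collection Visits.

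- HCC, weeks after the intervention: V2 at 4-6, V3 at 12-14. Shortest gap 12 − 6 = 6 weeks; longest 14 − 4 = 10 weeks.
- CCC, weeks after V1: V2 at 10-12, V3 at 18-20. Shortest gap 18 − 12 = 6 weeks; longest 20 − 10 = 10 weeks.

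**3. Illustration of the room left open**

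Taking each version's two outcomes at its own visit gives four candidate tests: systolic and diastolic pressure at V3, and hot flash frequency and severity at V2. The plan states no alpha, no correlations and no rule for combining tests. Assumptions: two-sided 0.05 per test, no true effect, the two pairs independent of each other, and success claimed if any test is significant.

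With independence throughout:

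- Two tests: 1 − 0.95² = 9.75%.
- Four tests: 1 − 0.95⁴ = 18.5%.

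With correlation ρ within each pair, let q(ρ) be the bivariate normal probability that both |Z| values are below 1.96. The chance of at least one false positive is 1 − q(ρ) for one pair and 1 − q(ρ)² for two.

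| ρ within pair | Two tests (hot flash pair) | Four tests |
|---|---|---|
| 0 | 9.75% | 18.5% |
| 0.5 | 9.1% | 17.3% |
| 0.9 | 7.0% | 13.6% |

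**4. Power**

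None can be reproduced. The plan gives no alpha, effect size or SD, and Number of Subjects says the enrolment figure was chosen arbitrarily.

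**The case against.** The contradiction itself cannot be argued away, but several points limit what follows from it.

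- **The error rates assume a rule the plan does not state.** Nothing says that all four tests will be run and any one counted as success. The count of four is also a choice: mixing endpoints and visits gives 4 outcomes × 2 visits = 8, and treating frequency and severity as one score gives fewer. This stands. The figures show how much room is left open, not the plan's error rate.
- **Hot flashes are not wholly without a method.** The Abstract, after stating the V1 to V2 comparison, refers to additional mean contrasts for later visits, which implies a mean contrast for the primary. Read literally, the analysis section would also treat hot flashes as one of the secondary outcomes. This stands in part: a method can be inferred, but primary status, the visit and the handling of two outcomes cannot.
- **NCC is a minor slip.** With two arms, no reader would mistake the comparator. This stands. Endpoint and visit carry the point.
- **The Overview may intend a single score.** Its wording can be read that way, so the two-test figure rests on an unsettled reading. This stands, and it is a reason to settle the matter in the text.
- **It is a pilot of arbitrary size.** That lowers the weight of any one p-value. However, the trial also aims to supply effect sizes for larger trials, and the plan must say for which outcome and at which visit.

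The section may have been carried over from a blood pressure study, but the documents do not say so. It remains the operative analysis text.

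**Conclusion.** The concern holds, and the plan must be corrected. The Statistical Analysis section is wrong as written, rather than merely short of detail: it gives primary status to the wrong endpoint at the wrong visit and leaves the declared primary outcome without a primary analysis. This rests on the text alone and needs no assumption.

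The size of the discrepancy is a different endpoint, a visit 6 to 10 weeks later for a given participant, and an undefined comparator label. The false-positive ranges, 7.0% to 9.75% for the hot flash pair and 13.6% to 18.5% for all four candidates, depend on the assumptions listed with the calculation and are secondary to the conclusion.

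**What to change.** Replace the two blood pressure sentences in the Statistical Analysis section with text such as:

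> Linear mixed models will be fitted to diary hot flash frequency and severity to compare HCC with CCC. The between-group contrast of the change from V1 (diary kept for the 7-14 days after V1) to V2 is the primary test of efficacy. Contrasts at V3, blood pressure and all other outcomes are secondary.

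Also state whether frequency and severity form one score or two primary tests and, if two, the multiplicity rule.

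While the section is open, a related gap can be closed. The daily severity score divides by that day's number of hot flashes (Menopause-related symptoms), so it is undefined on a day with none. Pilot frequency did reach 0 (Table 1). The pilot severity range also reaches 0 although the lowest category is 1, which suggests such days were scored 0, but that does not bind this trial. The SAP should say how they enter the score.

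The cost is SAP wording only: no new data, visits or participants. The change should be dated before outcome data are examined.
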